Scope of the Problem. Globally, fewer than 3% of age-eligible girls in low-income countries receive even a single dose of the HPV vaccines (27). Projecting current cervical cancer incidence and mortality trends in the face of low vaccine uptake, deaths from cervical cancer will increase dramatically in low-and middle-income countries over the next several years (28). Even in some wealthier nations, completion of even a two-dose vaccine series continues to be a problem. Thus, there is an urgent need to expedite the evaluation of a single dose of the prophylactic

HPV vaccine, to present the resulting evidence to regulatory and/or recommending bodies, and ultimately to ensure that more girls receive the vaccine.

Evidence and biological rationale supporting protection by a single dose of the HPV vaccine

The first line of evidence to support that HPV vaccines will induce long term protection after a single dose is the finding that the vaccines consistently induce strong and durable neutralizing antibody responses against the targeted types among individuals who received only a single dose. For Cervarix, the GMT antibody titers after four years were only four-fold lower in one dose compared to three dose recipients (29), and this ratio has been maintained out to seven years (30). For Gardasil, a similar four-fold difference between the antibody levels in the one and three dose recipients were reported in a four-year interim analysis (31). Note that we focus on the plateau levels of VLP antibodies and not peak titers immediately after the booster dose because the vast majority of exposures to sexually transmitted HPV infections will occur when vaccinated females are in the plateau phase. Further, in assessments of single- and multi-dose regimens of the HPV vaccines, peak titers do not predict plateau titers. Presently, direct comparison between the levels induced by different vaccine products among one-dose recipients is not possible because of the differences in study design, populations, and serologic assays used.

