Time since last dose: Among the women who receive three doses of Gardasil, the antibody levels peak immediately following the third vaccination and then decline to a more stable plateau. The boosting of the primary response generates a transient burst of antibodies, presumably due to the induction of short-lived plasma blasts from memory B cells, which transiently exaggerates the contribution of the booster doses to antibody titers.

Einstein and colleagues (49) show that, among approximately 100 women 18-26 year old who received three doses of Gardasil, the GMTs for HPV 16 antibodies decrease from 10053 at 7 months after the initial vaccination to 3265, 1183, 894, 653, and 750 at 12, 18, 24, 36, and 48 months after vaccination. Similarly, the GMTs for HPV 18 antibodies decrease from 2258 at 7 months to 596, 249, 175, 128, and 139 at 12, 18, 24, 36, and 48 months after vaccination.

We emphasize that no similar peak is observed after the first dose of Cervarix (Figure 1). To illustrate this, in the Costa Rica HPV Vaccine Trial (CVT) among women who received three doses, the HPV16 GMT one-month post dose one of Cervarix was 598; this increased after the second and third doses to 2035 at 12 months, and then decreased to 1115, 899, and 748 at 24, 36, and 48 months. For HPV18, the 1-month GMT was 224, which increased following the second and third dose to 826 at 12 months, and then decreased to 470, 369, and 334 at similar time points (n.b. antibody titers cannot be compared between studies due to profound differences in immunologic assays). In contrast, among women who received only a single dose, the GMTs for HPV 16 antibodies at 12 months after the first vaccination was 114 and remained stable at 124, 135, and 137 at 24, 36, and 48 months (Figure 1; Table 1). Among these same

women, the GMTs for HPV 18 antibodies at 12, 24, 36, and 48 months after vaccination was 70, 69, 73, and 70 (50). Given the association with time since vaccination and antibody titer, our evaluation is focused on antibody levels in the plateau phase (at least 24 or 36 months after vaccination), and not the peak titers, as we believe these are more relevant and predictive of long-term vaccine protection.

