- Blood collected within the predefined follow-up window. Denoting T_1 as the time of the first vaccination, the window for the 24-month visit is between T_1+700 days and T_1+912 days and the window for the 36-month window is T_1+1065 days and T_1+1278 days.
- No HPV vaccination outside of the study prior to blood collection. The participant did not report receiving an HPV vaccine and, among those tested, did not have HPV6 and HPV11 vaccine-level antibodies.

Note, the ATP cohort for a given analysis depends on both the timing of the analysis and the specified HPV type.

3b. Secondary/Exploratory Analytical Cohorts

We will also consider the: (i) modified Intention-to-Treat (ITT) cohort, including all participants receiving the correct number of doses and with blood collected during the predefined follow-up window; (ii) Seropositive-ATP (SP-ATP) cohort that includes participants who are seropositive at baseline, but otherwise satisfy the ATP requirements; and (iii) Serocombined-ATP (SC-ATP) cohort that combines the ATP and SP-ATP cohorts. Furthermore, for SO4, we will consider all

girls who are not seropositive at baseline, had blood collected between $T_1 + 14$ and $T_1 + 90$ days for the 1 month analysis and between $T_1 + 274$ and $T_1 + 547$ days for the 1 year analysis, and did not receive an HPV vaccination outside of the study prior to their blood collection. Additionally, we will test for HPV6/HPV11 antibodies in a subset of participants who are at-risk for external HPV vaccination or show serologic evidence of additional HPV vaccine doses.

4. Endpoints

The four endpoints are HPV-16 and HPV-18 specific antibody results obtained from blood specimens (serum) collected at the 24- (interim) and 36-(primary) month visit (i.e. 4 endpoints = 2 HPV types x 2 time-points). All antibody levels are measured by HPV type-specific ELISA. Two additional endpoints, HPV-16 and HPV-18 antibody levels measured from serum collected at the 1-month visit and the 1-year visit, will also be included to achieve Secondary Objective 4 (SO4).

5. Implementation of Analysis

The final 24- and 36-months analyses will be performed once the corresponding follow-up window for the last enrolled participant closes

6. Controlling the Type-I error rate

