The analysis defined in the following section ensures that under the null hypothesis of inferiority, the probability of declaring non-inferiority (i.e. type I error rate) is less than 0.025 for HPV-16 and HPV-18 endpoints, respectively.

7. Statistical Analyses for Immunogenicity

7a. Methods for The Primary Objective

We will estimate the GMT ratios for HPV-16 and HPV-18 at 24 and 36 months in the corresponding ATP cohort.

We define $R^H(t) = GMT_1^H(t)/GMT_3^H(t)$ to be the GMT ratio for HPV-H (i.e. HPV-16 or HPV-18) at time point t (i.e. 24 or 36 months) when comparing antibody levels in 9-14 year old girls receiving 1 dose of Cervarix to levels in 18-25 year old women receiving 3 doses of Gardasil.

We will estimate $R^H(t)$ by fitting a generalized estimating equation (GEE) model where the dependent variable is the log-antibody level and the independent variable is study-group. Denoting the estimated coefficient for study-group by $\hat{\beta}^H(t)$ and the corresponding robust standard error by $\hat{\sigma}^H(t)$, we define our estimate by $\hat{R}^H(t) = \exp(\hat{\beta}^H(t))$ and define the two-sided $(1-\alpha)\%$ confidence interval (CI), $(\hat{R}_{\alpha/2}^H(t), \hat{R}_{1-\alpha/2}^H(t))$, by $\exp(\hat{\beta}^H(t) \pm z_{1-\alpha/2} \hat{\sigma}^H(t))$, where $z_{1-\alpha/2}$ is the $1-\alpha/2$ quantile of a normal distribution. In the model, we will group girls into clusters of full siblings and use an exchangeable correlation matrix.

We will declare non-inferiority if $\min\left(\hat{R}_{0.005}^{16}(24), \hat{R}_{0.005}^{18}(24)\right) > 0.67$ or, upon failure of that criterion, $\min\left(\hat{R}_{0.02}^{16}(36), \hat{R}_{0.02}^{18}(36)\right) > 0.67$. Note, under the null hypothesis that both $\min(R^{16}(24), R^{18}(24)) < 0.67$ and $\min(R^{16}(36), R^{18}(36)) < 0.67$, the probability of declaring non-inferiority or the Type I error rate is less than 0.025.

7b. Methods for The Secondary Objectives

Secondary Objective 1 (SO1): For each combination of HPV-type, time-point, and study group, we will describe the distribution of antibody levels by showing the reverse cumulative distributions (i.e. 1-cumulative distribution function) in the ATP cohort.

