Secondary Objective 2 (SO2): For each combination of HPV-type, time-point, and study group, we will report the proportion of the ATP cohort who seroconvert (i.e. achieve HPV-16 or HPV-18 antibody levels greater than 1.41 international units (IU)/mL or 1.05 IU/mL, respectively) and exact 95% confidence intervals. For each HPV-type and time-point, we will assess whether seroconversion rates differ between study groups using fisher's exact test.

Secondary Objective 3 (SO3): We will repeat the analyses described for the primary objective and secondary objectives 1 and 2 restricted to 11-14-year-old girls. We will also perform a direct comparison of the antibody levels in 9-10 and 11-14 year old girls (e.g. compare GMT in GEE w/ age group as the independent variable, compare seroconversion rates by fisher's exact test).

Secondary Objective 4 (SO4): We will repeat the analyses described for the primary objective and secondary objectives 1 and 2 to compare antibody levels at 1-month and 1-year post-vaccination in girls 9-10 years old girls and in girls 11-14 years old.

Secondary Objective 5 (SO5): We will consider the following baseline covariates: age, enrollment date, and district. Within each study-group and at each time point, we will report the GMTs and their 95% CIs for HPV-16 and HPV-18 antibody levels in subgroups defined by these baseline covariates. Moreover, we will use GEEs to assesses the association between GMTs and these baseline covariates and show both reverse cumulative distributions and seroconversion rates by subgroup.

7c. Methods for Sensitivity and Exploratory Analyses

We will repeat the methods for the primary and secondary objectives using the ITT, SP-ATP, and SC-ATP cohorts instead of the ATP cohort.

We will repeat the methods for the primary and secondary objectives after removing potential outliers (e.g. participants potentially exposed to a vaccination outside of study) where the antibody level is $2 \times \text{IQR}$ above the 75th percentile.

We will assess whether antibody levels are changing over time. For each combination of study group and HPV type, we will compare GMTs at 24 and 36 months.

8. Statistical Analyses for Evaluating ELISA assays And Comparability with SEAP-NA

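### The SO4 1-month comparison of 9-10 with 11-14 year olds takes blood from day 14 to day 90 with no term for draw day; adding one is a cheap safeguard

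*SAP*

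**What the plan says.** SAP 3b defines the SO4 analysis set as girls not seropositive at baseline and without outside HPV vaccination before the draw, who "had blood collected between $T_1 + 14$ and $T_1 + 90$ days for the 1 month analysis" or "between $T_1 + 274$ and $T_1 + 547$ days for the 1 year analysis". SAP 7b then repeats the primary, SO1 and SO2 methods "to compare antibody levels at 1-month and 1-year post-vaccination in girls 9-10 years old girls and in girls 11-14 years old". In the primary method (SAP 7a), "the dependent variable is the log-antibody level and the independent variable is study-group", with clustering of full siblings. For SO4, age group takes the place of study group. Neither 7b nor 7c adds a draw-day covariate, a narrower-window repeat or a summary of draw timing. SO5 looks at age, enrollment date and district, but only at 24 and 36 months.

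The protocol's background (Time since last dose) reports that, in the Costa Rica trial, "the HPV16 GMT one-month post dose one of Cervarix was 598" among women who went on to three doses; the HPV18 figure is 224. In other women, who had a single dose, HPV16 GMTs at 12, 24, 36 and 48 months were 114, 124, 135 and 137, and HPV18 GMTs were 70, 69, 73 and 70. On the single-dose evidence, the protocol also states that "in assessments of single- and multi-dose regimens of the HPV vaccines, peak titers do not predict plateau titers".

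**The concern.** The month-1 GMTs are well above the flat values seen from month 12, so the 1-month sample is probably taken while titres are still changing. A window 76 days wide then mixes girls at different points on that curve. If one age group is drawn later on average, part of any age difference in GMT reflects timing, and a real age difference could equally be masked. The model cannot separate the two.

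The stake is limited but real. Both documents say that SO3 and SO4 are there partly because the national programme targets 10-year-olds, so the comparison of 9-10 with 11-14 year olds will be read for reassurance that the younger girls respond like the older ones. It should not carry an avoidable source of bias. Nor, given the protocol's own statement about peak and plateau, should agreement at month 1 be read as agreement at 24 or 36 months.

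**Working it through.** **1. The protocol's SO4 precision reproduces.** Inputs from Power and Sample Size Considerations: 173 and 347 girls, 5% seropositive, 10% missing the 1-month visit, SD 1.38 on the log scale.

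- n₁ = 173 × 0.95 × 0.90 = 147.9; n₂ = 347 × 0.95 × 0.90 = 296.7
- SE = 1.38 × √(1/147.9 + 1/296.7) = 0.139
- 95% CI around a ratio of 1: exp(±1.96 × 0.139) = 0.76 to 1.31, length 0.55, as stated.

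This calculation has no timing component.

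**2. Size of the apparent fall.** HPV16: 598/114 = 5.2. HPV18: 224/70 = 3.2. These are ratios between two sets of women over 11 months. They are not an observed fall within day 14 to day 90.

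**3. Effect of unequal draw timing.** The documents give no GMT between month 1 and month 12 after a single dose, so the shape of the fall has to be assumed. Let the log titre fall at slope s per day. If 9-10 year olds are drawn k days later on average, the ratio is multiplied by exp(−s·k); if earlier, by exp(s·k). For a log-linear fall from day 30 to day 365:

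- HPV16: s = ln(598/114)/335 = 0.00495
- HPV18: s = ln(224/70)/335 = 0.00347

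The two faster cases put the whole fall into 150 days (complete by day 180) or 60 days (complete by day 90). For k = 10:

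| Assumed course of the fall | HPV16 ratio × | HPV18 ratio × |
|---|---|---|
| Log-linear, day 30 to 365 | 0.952 (5% lower) | 0.966 (3% lower) |
| Complete by day 180 | 0.895 (10% lower) | 0.925 (7% lower) |
| Complete by day 90 (extreme) | 0.759 (24% lower) | 0.824 (18% lower) |

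In the first case the shift is 0.0495/0.139 = 0.36 of a standard error for HPV16 and 0.0347/0.139 = 0.25 for HPV18. With k = 0 the bias is zero in every row.

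**4. Effect on precision when timing is equal.** Draw days spread evenly over day 14 to 90 add variance (76s)²/12. For HPV16 in the log-linear case the SD becomes √(1.38² + 0.376²/12) = 1.384 and the CI 0.761 to 1.314, essentially unchanged. Complete by day 180 gives 0.759 to 1.318; the extreme case gives 0.743 to 1.346.

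**5. The 1-year window.** It spans 547 − 274 = 273 days. If the log-linear fall really ran to day 365, a day-274 sample would exceed a day-365 sample by exp(0.00495 × 91) = 1.57-fold (HPV16) or exp(0.00347 × 91) = 1.37-fold (HPV18). If the plateau is reached sooner the difference is smaller, and from month 12 the quoted single-dose GMTs are flat. An adjustment made at 1 month should therefore be made at 1 year too.

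**The case against.** The strongest reply is that no bias has been shown. Both age groups attend the same 1-month visit under the same window, so draw days may well match. A reader might infer unequal timing from the protocol Overview, which provides for stopping enrolment of 9- and 10-year-olds once the national programme starts. That concerns the calendar date of entry, not the interval from vaccination to draw, and it does not imply different draw days. This part of the reply stands: the risk is conditional.

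Three other readings are tempting and are not supported.

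- *The protocol's data show a 3- to 5-fold fall after month 1.* The ratios are correct, but the month-1 and month-12 values come from different women. The month-1 sample was taken after one dose only, so the comparison is reasonable, but it is not a within-group fall. Nothing dates the fall more closely than by month 12, and the data are from women, not girls.
- *The statement* "We emphasize that no similar peak is observed after the first dose of Cervarix" *contradicts those figures.* The comparator is three-dose Gardasil in the preceding paragraph, where HPV16 goes from 10053 at month 7 to 653 at month 36, a ratio of 15.4. A ratio near 5 is compatible with the word similar, and the supporting figure is not available here. No correction is called for.
- *The month-1 comparison is the trial's evidence on plateau titres in 9-10 year olds.* No current text says so. SO4 already has a 1-year comparison, SO3 in SAP 7b already adds a direct comparison of the two age groups, and the protocol gives only an expected confidence interval for the 1-month analysis, with no decision rule.

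What survives is that draw day can matter in this window, the model leaves it out, and including it is almost free.

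**Conclusion.** The point holds as a minor improvement to a secondary analysis. The 1-month SO4 ratio is open to bias if mean draw day differs by age group: about 5% (HPV16) or 3% (HPV18) for a 10-day difference under a log-linear fall to day 365, and more if the fall comes earlier. This rests on three assumptions: that the two sets of women can be joined into one curve, that girls decline in a similar way, and that a timing difference exists at all. Without such a difference there is no bias and, outside the extreme case, almost no loss of precision. The primary analysis is not affected. On the protocol's own statement about peak and plateau, the 1-month result is best read as descriptive, with weight on the 1-year and SO3 age comparisons already planned.

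**What to change.** In SAP 7b, under SO4:

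1. Report the distribution of days from vaccination to draw by age group, at 1 month and at 1 year.
2. Add days since vaccination as a covariate in the SO4 GEE at both time points, either as the main model or as a sensitivity model beside the unadjusted one. A second (curved) term may be allowed, since the course of titres within the window is unknown.
3. State that the 1-month comparison is descriptive, and that any statement about later titres in 9-10 year olds draws on the 1-year comparison and the SO3 age comparison.

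The cost is SAP wording, one extra model and one or two degrees of freedom. Draw dates are already needed to apply the windows, so no new data are required. The background section on titres over time needs no change.

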At peak levels one-month after the third dose of Gardasil, Block et al (43) demonstrated that GMTs for HPV-16 and HPV-18 were, respectively, **1.8x** (1.5-2.2) and 2.0x (1.7-2.4) higher in girls 10-15 years old as compared with girls/women 16-23 years old.

When focusing on girls within the 9-14 year old range, there is no evidence to suggest that antibody levels dramatically increase at menarche. Reisenger and colleagues (54) reported that GMTs for HPV-16 and HPV-18 were 1.5x and 1.6x higher in girls 9-12 years old as compared to girls 13-15 years old at 1 month after last vaccination among 3-dose recipients of Gardasil. Others (unpublished data, personal communication) have similarly found that the immune response is similar pre/post-menarche.

HPV serostatus at time of initial vaccination: Finally, HPV serostatus at the time of HPV vaccination (i.e.: due to natural infection) does impact vaccine-induced plateau level. Petersen et al (55) reported that, among women who received three doses of Gardasil-9 in the per protocol population, HPV16 antibody titers 36-months after initial vaccination were 3.2x lower compared to HPV16 seropositive/HPV16 DNA negative women. This latter group comprised ~12% of the total study population and were excluded in the evaluations for licensure of the Merck HPV vaccines.

Figure 1. HPV 16 and 18 GMTs by months and number of doses of Cervarix (adapted from ref (50))

[figure not shown]

Table 1. GMT ratios of the antibody response to HPV vaccination by number of doses administered, the time since last dose, the vaccine product, and age and serostatus at first vaccination.

HPV type	Vaccines (Source)	# of doses	Comparison groups	# of months post vaccination		
				7	24	36
				Ratio (95% CI)	Ratio (95% CI)	Ratio (95% CI)
Studies comparing GMTs between number of vaccine doses						
HPV-16	Cervarix †	1, 3	3 doses vs. 1	9.1 (6.5-12.5) †	9.1 (6.5-12.5) †	6.6 (4.8-9.0) †
HPV-18	Cervarix †	1, 3	3 doses vs. 1		6.9 (5.0-9.4) †	4.8 (3.5-6.4) †
Studies comparing GMTs by vaccine product						
HPV-16	Cervarix & Gardasil (49)	3	Cervarix vs. Gardasil	4.3 ‡**	5.8 (4.0-8.5)	5.9 (3.9-9.4)
	Cervarix & Gardasil (52)	3	Cervarix vs. Gardasil			
HPV-18	Cervarix & Gardasil (49)	3	Cervarix vs. Gardasil	6.6 ‡**	9.4 (6-14)	12.5 (8.0-19.4)
	Cervarix & Gardasil (52)	3	Cervarix vs. Gardasil			
Studies comparing GMTs across age groups						
HPV-16	Gardasil (43)	3	10-15 vs. 16-23 y/o	1.8 (1.5-2.2)		
	Cervarix (53)	3	10-14 vs. 15-25 y/o	2.4 (1.6-3.5)		

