Because the national vaccination program has been initiated, there is the potential that some girls enrolled at ages 9-10 years may have received an additional vaccination dose but have failed to report it. Therefore, we plan to conduct the following secondary/sensitivity analysis. We will compare GMTs, distributions, and seroconversion rates for HPV-16 and HPV-18 antibodies, assessed at 24 and 36 months after initial vaccination, between 11-14 year old girls receiving 1 dose of Cervarix and 18-25 year old women receiving 3 doses of Gardasil. We will also calculate the GMT ratios, comparing girls 9-10 years old at vaccination with girls 11-14 years old at vaccination, and their 95% confidence intervals for HPV-16 and HPV-18 antibody levels at 1 month and 1-year post-vaccination. Additionally, we will test for HPV6/HPV11 antibodies in a subset of participants who are at-risk for external HPV vaccination or show serologic evidence of additional HPV vaccine doses.

Power and Sample Size Considerations

We calculate the power to show non-inferiority at 24 months and the power to show non-inferiority at 36 months given that we enroll 520 women 18-25 year old and 347 girls 9-14 year old. Specifically, we assume that $\hat{\sigma} = 1.38$, 20% of all 18-25 year old women do not receive all 3 doses, 100% of 9-10 year old girls (i.e. worst case scenario) receive a vaccination outside the study, 20% of all participants are lost-to-follow up, 10% of the 18-25 year old women are seropositive at baseline, 5% of the 11-14 year old girls are seropositive at baseline, the common true ratio, R, for HPV-16 and HPV-18 is 1, and the non-inferiority threshold (t) is 0.67, in accordance with the recommendation of the WHO Expert Committee on Biological Standardization(60). Based on these assumptions, we will have 65% power to demonstrate non-inferiority at 24 months and 84% power to demonstrate non-inferiority at 36 months. Power calculations for other values of R and t are listed in table 4. Note the power reported for 36 months is $\Pr(\min(\hat{R}_{0.02}^{16}(36), \hat{R}_{0.02}^{18}(36)) > t)$, a lower bound for the probability of rejecting non-inferiority at either the 24- or 36- month analysis. In the more optimistic scenario, where 9-10 year old participants do not receive vaccinations outside the study, our power increases to 78% at 24 months and 91% at 36 months.

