**Statistical Analysis Plan to Address the Primary and Secondary Objectives for the Trial
Entitled**

“Non-inferiority trial comparing immunogenicity from 1-dose of bivalent HPV vaccine in girls to 3-doses of quadrivalent vaccine in women: The PRIMAVERA-ESCUUDO Trial (‘Puente de Respuesta Inmunológica para Mejorar el Acceso a Vacunas y Erradicar el cancer’)”

(NCI Protocol 19-C-009)

Date: February 28, 2023

ClinicalTrials.gov ID: NCT03728881

Table of Contents

1. Introduction	3
2. Objectives	3
2a. Primary Objective	3
2b. Secondary Objectives	3
3. Analytical Cohorts	4
3a. Primary Analytical Cohort	4
3b. Secondary/Exploratory Analytical Cohorts	4
4. Endpoints	5
5. Implementation of Analysis	5
6. Controlling the Type-I error rate	5
7. Statistical Analyses for Immunogenicity	5
7a. Methods for The Primary Objective	5
7b. Methods for The Secondary Objectives	6
7c. Methods for Sensitivity and Exploratory Analyses	6
8. Statistical Analyses for Evaluating ELISA assays	7

1. Introduction

This document describes the pre-planned analysis for the trial entitled “**Non-inferiority trial comparing immunogenicity from 1-dose of bivalent HPV vaccine in girls to 3-doses of quadrivalent vaccine in women**”.

2. Objectives

2a. Primary Objective

Primary Objective (PO): To demonstrate that the immunogenicity (as determined by ELISA) of a single dose of Cervarix in 9-14 year old girls is non-inferior to the immunogenicity of three doses of Gardasil, administered at 0, 2, and 6 months, in 18-25 year old women 36 months after initial vaccination, with an interim analysis at 24 months after initial vaccination.

Either of following criteria will qualify as non-inferiority:

- The interim analysis will assess non-inferiority at 24 months. Non-inferiority will be demonstrated if the lower limits for the two-sided 99% confidence intervals of the GMT ratios (1-Dose Cervarix divided by 3-Doses of Gardasil at 24 months) for both HPV-16 and HPV-18 antibody levels exceed 0.67.
- The primary analysis will assess non-inferiority at 36 months. Non-inferiority will be demonstrated if the lower limits for the two-sided 96% confidence intervals of the GMT ratios (1-Dose Cervarix divided by 3-Doses of Gardasil at 36 months) for both HPV-16 and HPV-18 antibody levels exceed 0.67.

2b. Secondary Objectives

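### The serocombined and modified ITT repeats of the non-inferiority analysis leave baseline serostatus out of the model, although the plan expects it to differ between groups and to raise titres; an adjusted estimate should be added.

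*SAP*

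**What the plan says.** The primary analysis uses participants seronegative at baseline for the HPV type analysed (Protocol, Primary Analytical Cohort; SAP 3a). In the GEE of SAP 7a, "the dependent variable is the log-antibody level and the independent variable is study-group". Both HPV types must pass. The rule looks at the "lower limits for the two-sided 99% confidence intervals of the GMT ratios" at 24 months and the "lower limits for the two-sided 96% confidence intervals of the GMT ratios" at 36 months, and in the power section "the non-inferiority threshold (t) is 0.67".

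SAP 3b defines three further cohorts: modified ITT (correct number of doses and blood drawn in the window, with no serostatus restriction), SP-ATP (seropositives only), and the "Serocombined-ATP (SC-ATP) cohort that combines the ATP and SP-ATP cohorts". For these, SAP 7c says: "We will repeat the methods for the primary and secondary objectives using the ITT, SP-ATP, and SC-ATP cohorts instead of the ATP cohort". The covariates examined under Secondary Objective 5 are age, enrollment date and district; serostatus is not among them.

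The protocol's background states that "HPV serostatus at the time of HPV vaccination (i.e.: due to natural infection) does impact vaccine-induced plateau level". Its power section assumes that "10% of the 18-25 year old women are seropositive at baseline, 5% of the 11-14 year old girls are seropositive at baseline".

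**The concern.** The groups are not randomised. The plan names a determinant of the plateau titre, expects it to be twice as common in women as in girls, and omits it from the model in the cohorts that include both strata. Prior infection in the older group then tends to pull the girls-to-women ratio down with no change in what either regimen does in seronegatives. SC-ATP is larger than ATP and should be the more precise check. If it misses 0.67 where ATP passes, a regulator may doubt the primary result for a reason the protocol already foresees. SP-ATP, where the same rule is repeated, will be very small.

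**Working it through.** **Inputs.** From the protocol's power section: log-titre SD 1.38; 520 women and 347 girls (the worst case, in which all 9-10 year olds are vaccinated outside the study); 20% of women without three doses; 20% lost to follow-up; 10% and 5% seropositive; true ratio 1; margin 0.67. From Table 1, seropositive/seronegative titre ratios (folds) for HPV-16 and HPV-18: 3.8 and 2.0 after one Cervarix dose, 3.2 and 5.0 after three Gardasil-9 doses.

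**Step 1: reproduce the stated power.** Evaluable in ATP: women 520 × 0.8 × 0.8 × 0.9 = 299.5; girls 347 × 0.8 × 0.95 = 263.7. SE = 1.38 × √(1/299.5 + 1/263.7) = 0.1165. Pass probability per type = Φ((ln ratio + 0.4005)/SE − z), where 0.4005 = −ln 0.67 and z = 2.576 (24 months) or 2.054 (36 months). This gives 0.805 and 0.917. Squared, with the two types taken as independent, the joint power is 0.65 and 0.84, as the protocol states.

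**Step 2: SC-ATP, unadjusted.** Women 520 × 0.64 = 332.8; girls 347 × 0.8 = 277.6. Expected ratio = exp(0.05 × ln fold in girls − 0.10 × ln fold in women):
- HPV-16: exp(0.05 × ln 3.8 − 0.10 × ln 3.2) = 0.952
- HPV-18: exp(0.05 × ln 2.0 − 0.10 × ln 5.0) = 0.881

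Adding the mixture variance p(1−p)(ln fold)² to 1.38² in each group gives SEs of 0.1151 and 0.1156. At 36 months the types pass with probability 0.840 and 0.625, jointly 0.53.

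**Step 3: serostatus as a main effect.** Stratum weights n₁n₃/(n₁+n₃), with n₁ girls and n₃ women, are 140.2 (seronegative) and 9.8 (seropositive). Table 1 implies seropositive ratios of 3.8/3.2 = 1.19 and 2.0/5.0 = 0.40. The pooled ratios are 1.011 and 0.942, and the SE is 1.38/√150.0 = 0.1127.

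| SC-ATP, true seronegative ratio 1 | 24 months | 36 months | 36 months, 520 girls |
|---|---|---|---|
| Unadjusted | 0.29 | 0.53 | 0.64 |
| Serostatus in model | 0.58 | 0.79 | 0.87 |
| No serostatus effect | 0.71 | 0.88 | 0.94 |

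**Step 4: split the shift.** Case mix only (same fold in both groups, 5% against 10%): ratios 0.944 and 0.923 with the women's folds, 0.935 and 0.966 with the girls' folds; 36-month power 0.62 and 0.70. Equal prevalence of 7.5% with the Table 1 folds: the HPV-18 ratio is still exp(0.075 × ln(2.0/5.0)) = 0.934, and power is 0.75. In logs that is 0.069 of a total HPV-18 shift of 0.126, about half.

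**Step 5: vary the inputs (36 months, 347 girls, unadjusted).**
- True ratio 1.14: power 0.91. True ratio 1.77: above 0.99.
- 12% of women seropositive (the share the protocol quotes from the Gardasil-9 analysis): 0.40.
- Women's folds 1.5 and 1.7 (three-dose Cervarix, Table 1): ratios 1.03 and 0.98, power 0.87.

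**Step 6: SP-ATP.** Girls 347 × 0.8 × 0.05 = 14, or 520 × 0.8 × 0.05 = 21; women 332.8 × 0.10 = 33. SE = 0.44 or 0.39. To pass at 36 months the observed ratio must exceed 0.67 × exp(2.054 × SE), about 1.7 or 1.5. At a true seropositive ratio of 1, each type passes in about 13-15% of trials.

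**The case against.** A reader might infer that these repeats can fail from case mix alone. The figures do not support that. Case mix moves the ratio by about 3-8%, far from 0.67, so failure also needs a true ratio near 1 and sampling error. About half of the HPV-18 shift is a different serostatus effect by regimen, which a main effect does not remove; hence 0.79 rather than 0.88 after adjustment.

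A reader might also infer that the repeats would often contradict a successful primary result. That holds only near a ratio of 1. In simulated trials with ATP and SC-ATP drawn from the same participants, SC-ATP failed after ATP had passed in 38% at a ratio of 1, under 10% at 1.14 and none at 1.77. The protocol's background predicts ratios above 1.14 at 24 months and above 1.77 at 36 months. However, 1 is the value on which the trial was powered.

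The choice of folds matters. Neither Gardasil-9 (a fallback only) nor three-dose Cervarix is the planned comparator, and the second choice almost removes the problem. The SC-ATP figures also do not carry over to modified ITT. Outside vaccination is not stated as an exclusion there, and any extra doses in girls would push the ratio up.

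Two further points stand. The SAP labels these analyses sensitivity or exploratory, ties no decision to SC-ATP or modified ITT, and shows both strata through ATP and SP-ATP. The unadjusted pooled ratio is also a legitimate all-comers quantity. But SP-ATP is too small to explain a discordant SC-ATP result, and the all-comers ratio alone does not separate vaccine effect from prior infection.

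**Conclusion.** The point holds as a worthwhile improvement to secondary analyses, not as a flaw in the primary test. At the planning ratio of 1, with the Gardasil-9 folds, the unadjusted SC-ATP repeat has 36-month joint power of about 0.53, against 0.79 adjusted and 0.88 with no serostatus effect. The loss is minor when the true ratio is well above 1, and it nearly disappears with the three-dose Cervarix folds. For modified ITT only the omission is established; its net direction is unknown. The ATP conclusion is unaffected.

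The size rests on these assumptions: Gardasil-9 folds stand in for Gardasil; the one-dose Cervarix folds apply to girls and at both time points (the columns of Table 1 are not legible enough to confirm a 36-month value); the 5% stated for 11-14 year olds applies to all girls; and the two HPV types are independent, as the stated power requires.

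**What to change.** In SAP 7c, for SC-ATP and modified ITT, add type-specific baseline serostatus to the GEE, or standardise both groups to a common serostatus mix. Report the group-by-serostatus interaction, since a main effect does not capture a different serostatus effect by regimen. Keep the unadjusted ratio beside it, labelled as the all-comers description. For SP-ATP, report the GMTs and the ratio with its confidence interval, and state that the 0.67 rule is not applied.

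The cost is SAP wording and one covariate. Baseline serology is already needed to define the ATP cohort, so no new data are required, and the primary analysis and its error control do not change.
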